Non-interventional Study Protocol

| | |
|---|---|
| Document Number: | TBD |
| BI Study Number: | 1237-0086 |
| BI Investigational Product(s): | Tiotropium/olodaterol (Spiolto®) |
| Title: | Taiwan Outcomes and Real-world Treatment Options for Chronic Obstructive Pulmonary Disease (TOReTO) |
| Brief lay title | A study in Taiwan based on medical records that looks at the occurrence of flare-ups in patients with chronic obstructive pulmonary disease (COPD) who started LABA/LAMA or LAMA treatment |
| Protocol version identifier: | V1.0 |
| Date of last version of protocol: | 25 November 2019 |
| PASS: | No |
| EU PAS register number: | TBD |
| Active substance: | R03AL06-olodaterol and tiotropium bromide |
| Medicinal product: | tiotropium/olodaterol |
| Product reference: | EMEA/H/C/003821 (EMA agency product number) FDA reference ID: 3643917 |
| Procedure number: | Not applicable |
| Marketing authorisation holder(s): | This study is initiated, managed, and financed by: [REDACTED] [REDACTED] [REDACTED] |
| Joint PASS: | No |
| Research question and objectives: | The primary objective is to understand the occurrence of COPD exacerbations in patients treated with LABA/LAMA in the routine clinical practice in Taiwan. The secondary objectives are to realize the clinical characteristics and prescription patterns for the COPD population in Taiwan. |
| Country(-ies) of study: | Taiwan |

Proprietary confidential information © 2019 Boehringer Ingelheim International GmbH or one or more of its affiliated companies

| | |
|---|--|
| Author: | 
[REDACTED]
 
Title: [REDACTED]
 
Name: [REDACTED]
 
Tel: [REDACTED]
 
Direct Line: [REDACTED]
 
Fax: [REDACTED]
 
[REDACTED]
 |
| Marketing authorisation holder(s): | 
[REDACTED]
 
Title: [REDACTED]
 
Name: [REDACTED]
 
Tel: [REDACTED]
 
Direct Line: [REDACTED]
 
Fax: [REDACTED]
 
Address: [REDACTED]
 
[REDACTED]
 
[REDACTED]
 |
| In case of PASS, add: MAH contact person: | Not applicable |
| In case of PASS, add: <EU-QPPV:> | Not applicable |
| In case of PASS, add: <Signature of EU-QPPV:> | Not applicable |
| Date: | 25 November 2019 |
| Page 2 of 41 | |

2. LIST OF ABBREVIATIONS

| | |
|------------------|--|
| ACOS | Asthma-COPD Overlap Syndrome |
| ADR | Adverse Drug Reaction |
| AE | Adverse Event |
| AESI | Adverse Event of Special Interest |
| BI | Boehringer Ingelheim |
| BMI | Body Mass Index |
| CA | Competent Authority |
| CAT | COPD Assessment Test |
| CI | Confidence Interval |
| COPD | Chronic Obstructive Pulmonary Disease |
| CRF | Case Report Form |
| CRO | Contract Research Organization |
| CT | Computed Tomography |
| e.g. | Exempli Gratia |
| etc. | ET Cetera |
| DVP | Data Validation Plan |
| EMA | European Medicines Agency |
| ENCePP | European Network of Centres for Pharmacoepidemiology and Pharmacovigilance |
| FDA | Food and Drug Administration |
| FDC | Fixed-dose Combination |
| FEV ₁ | Forced Expiratory Volume in one second |
| FVC | Forced Volume Vital Capacity |
| GCP | Good Clinical Practice |
| GEP | Good Epidemiological Practice |
| GERD | GastroEsophageal Reflux Disease |
| GI | GastroIntestinal |
| GPP | Good Pharmacoepidemiology Practice |
| GVP | Good Pharmacovigilance Practices |
| GOLD | the Global Initiative for Chronic Obstructive Lung Disease |
| ICD | The International Classification of Diseases |
| ICH | The International Conference on Harmonisation |
| ICS | Inhaled Corticosteroids |
| IEC | Independent Ethics Committee |
| IPPV | Intermittent Positive Pressure Ventilation |
| IRB | Institutional Review Board |
| LABA | Long-Acting Beta-Agonist |
| LAMA | Long-Acting Muscarinic Antagonist |
| MAH | Marketing Authorisation Holder |
| mMRC | modified Medical Research Council dyspnea scale |
| NIS | Non-Interventional Study |
| NIPPV | NonInvasive Positive Pressure Ventilator |
| Olo | Olodaterol |
| PASS | Post-Authorization Safety Study |
| SABA | Short-Acting Beta-Agonist |
| SADR | Serious Adverse Drug Reaction |
| SAMA | Short-Acting Muscarinic Antagonist |

Proprietary confidential information © 2019 Boehringer Ingelheim International GmbH or one or more of its affiliated companies

SOP Standard Operating Procedure
Tio Tiotropium
WHO World Health Organization

Proprietary confidential information © 2019 Boehringer Ingelheim International GmbH or one or more of its affiliated companies

4. ABSTRACT

| | | | |
|---|--|---------------------------------|---|
| Name of company: Boehringer Ingelheim | | | |
| Name of finished medicinal product: Spiolto® (tiotropium/olodaterol) | | | |
| Name of active ingredient: tiotropium/olodaterol (ATC code: R03AL06; long-acting bronchodilators; a muscarinic receptor antagonist for tiotropium and a β adrenoreceptor agonist for olodaterol) | | | |
| Protocol date: 18 June 2019 | Study number: 1237-0086 | Version/Revision: 1.0 | Version/Revision date: 25 November 2019 |
| Title of study: | Taiwan Outcomes and Real-world Treatment Options for Chronic Obstructive Pulmonary Disease | | |
| Rationale and background: | 
Recently, more and more randomized controlled trials (RCT) demonstrated effectiveness of dual bronchodilators for the treatment of chronic obstructive pulmonary disease (COPD). DYNAGITO trial¹ has provided further evidences for tiotropium + olodaterol (Tio + Olo) compared with tiotropium in reducing moderate/severe exacerbations. In the real-world setting in Taiwan, the medication environment and electronic medical charts are well-established in medical centers. Hence, retrospective analysis is fully possible. Boehringer Ingelheim (BI) Taiwan and clinical practitioners' common goal are to adopt optimal treatment for COPD patients diagnosed per GOLD guideline.
 
So far, we can refer to some head to head studies examining the impact on lung function of various LABA/LAMA combinations; however, there is no study observing real world outcomes on prevention/risk reduction of acute exacerbations in Taiwan. The extent of outcomes from Tio + Olo (Spiolto®), other LABA/LAMA fixed-dose combinations [FDC]/free combos, or LAMA treatment of benefit for COPD patients in reducing acute exacerbation, is of great interest to explore.
 | | |
| Research question and objectives: | 
The primary objective is to understand the occurrence of COPD exacerbations in patients treated with LABA/LAMA or LAMA in the routine clinical practice in Taiwan.
 
The secondary objectives are to realize the clinical characteristics and prescription patterns for the COPD population in Taiwan.
 | | |
| Study design: | 
This is a retrospective, multi-center, cohort study to collect the data on COPD patients who were administered with LABA/LAMA (FDC or free combo) or LAMA treatment for 3 months at least prior to 30 June 2018. For LABA/LAMA therapy, new initiation or switching from other therapy (i.e., single/dual/triple) are both acceptable; for LAMA
 | | |

Proprietary confidential information © 2019 Boehringer Ingelheim International GmbH or one or more of its affiliated companies

| | |
|--------------------|---|
| | 
treatment, only new initiation will be acceptable. The data abstracted from eligible patients will be recorded only when they are available in the medical chart and will be categorized into the cohort A (patients treated with Tio + Olo), B (patients treated with other LABA/LAMA therapy), and C (LAMA therapy).
 
The follow-up period for each patient will be from the index date* until the date of death or 1 year after the index date, whichever occurs first. Patients will be censored at the time from one LAMA/LABA or LAMA switched to another LAMA/LABA or ICS.
 
*Index date: It is defined as the date of COPD patients in the cohort A and B starting using LABA/LAMA therapy regardless of new initiation or switching from other single/dual/triple treatment, or the date of the patients in the cohort C starting using LAMA treatment.
 |
| Population: | 
This study plans to review the medical chart from approximately 1,800 COPD patients receiving LABA/LAMA or LAMA treatment for 3 months at least prior to June 30 2018 in Taiwan.
 
Inclusion criteria
 
Patients who fulfil ALL the following criteria are included.
 
1. Patients who diagnosed with COPD who were prescribed with LABA/LAMA (FDC or free combo) as a new initiation or switching from other therapy (i.e., single/dual/triple), or newly receiving LAMA treatment for 3 months at least prior to 30 June 20182. Male or female patients ≥ 40 years of age 
Exclusion criteria
 
Patients who meet the following criterion are not included.
 
1. Patients with documented diagnosis of bronchial asthma, asthma-COPD overlap syndrome (ACOS), bronchiectasis, cystic fibrosis, or lung cancer |
| Variables: | 
Variables
 
• Patient demographics (date of birth, gender, race, body mass index [BMI], family history, occupation, etc.)• Diagnosis of COPD (date of diagnosis, disease severity, etc.)• Smoking status• Spirometry data (e.g., FEV₁, FVC)• COPD assessments (e.g., CAT, mMRC)• Acute exacerbations from 1 year before the index date until 1 year after the index date or the date of death (onset/stop date, etc.)• Hospitalizations due to COPD exacerbation (e.g., admission/discharge date, treatments)• Laboratory data (e.g., eosinophil counts) |

Proprietary confidential information © 2019 Boehringer Ingelheim International GmbH or one or more of its affiliated companies

| | |
|-----------------------|--|
| | 
• Pharmacological/non-pharmacological treatments from 6 months before the index date to 1 year after the index date or the date of death, especially for the following:
- Treatment related to COPD (start/stop dates, dosage, frequency, etc.)- Rescue treatments for COPD (antibiotics, oral corticosteroid, ventilator support, etc.)- Oxygen therapies- Surgeries for COPD therapy or improvement of lung function• Time/reasons for treatment switching (e.g., single/dual/triple therapy to LABA/LAMA prior to the index date, Tio + Olo to other therapies, single/dual escalating to dual/triple therapy)• Comorbidities (cardiovascular, cerebrovascular, respiratory, hepatic, renal, gastrointestinal, metabolic, infectious comorbidities, etc.) |
| | 
Primary outcomes
 
• Time to the first moderate or severe COPD exacerbation |
| | 
Secondary outcomes
 
• Annualized rate of mild/moderate/severe exacerbation• Time/reason (e.g., severe airflow limitation, diagnosis of asthma, worsening exacerbation) from LABA/LAMA escalating to LABA/LAMA/ICS or from LAMA to dual therapy• Percentage of patients receiving LABA/LAMA switched to triple therapy or LAMA switched to dual therapy• Change in pulmonary function after LABA/LAMA or LAMA initiation• Use of rescue medications |
| Data sources: | Source data are collected from medical charts in 12 medical hospitals in Taiwan. The case report form (CRF) will be designed for the data collection. |
| Study size: | Approximately 1,800 eligible COPD patients are planned to be enrolled from 12 medical hospitals in Taiwan. |
| Data analysis: | A Data Validation Plan (DVP) will be prepared to describe the processes for data validation. The data abstracted from the medical chart will be described with number, mean, standard deviation (SD), range, and 95% confidence intervals (95% CI) for continuous variables, and frequencies and percentages for categorical variables. |

Proprietary confidential information © 2019 Boehringer Ingelheim International GmbH or one or more of its affiliated companies

| | |
|--------------------|--|
| | 
The propensity score matching approach* will be used to balance the baseline characteristics between the study cohorts (Tio + Olo vs. other LABA/LAMA vs. LAMA therapy).
 
These data will be compared descriptively between patients receiving different regimens (Tio + Olo vs. other LABA/LAMA vs. LAMA therapy). If the propensity score matching is done, the difference before and after matching will be considered both.
 
The annualized rate of exacerbation with various severities will be calculated for each study group (episodes/patient-year), and the differences between the three cohorts will be compared by rate ratio.
 
Time to the first moderate or severe COPD exacerbation or escalating to dual or triple therapy will be compared between different cohorts using Kaplan-Meier curves with the incidence and time to events, and statistical significance will be assessed using log-rank tests.
 
Chi-square test or Fisher's exact test will be applied for categorical variables such as reasons for switching/escalating therapies, frequency, and percentage, etc.
 
*NOTE: Variables may include but not limited to age, gender, disease duration before index date, smoking status, body mass index, COPD assessment score (e.g., CAT and mMRC), spirometry data (e.g., FEV₁), oxygen therapy, comorbidities, disease severity, previous exacerbation, previous treatments, or eosinophil counts, where appropriate.
 |
| Milestones: | 
Planned the start of data collection: July 2019
 
Planned the end of data collection: November 2019
 
Planned final study report: the end of January 2020
 |

Proprietary confidential information © 2019 Boehringer Ingelheim International GmbH or one or more of its affiliated companies

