9.2.2 Study population

The data will be retrospectively abstracted from the medical chart after eligibility assessment. Eligible patients will be categorized into the cohort A (patients treated with Tio + Olo), B (patients treated with other LABA/LAMA therapy), and C (patients treated with LAMA therapy).

Inclusion criteria

Patients who fulfil **ALL** the following criteria are included.

1. Patients who diagnosed with COPD who were prescribed with LABA/LAMA (FDC or free combo) as a new initiation or switching from other therapy (i.e., single/dual/triple), or newly receiving LAMA treatment for 3 months at least prior to 30 June 2018
2. Male or female patients ≥ 40 years of age

Exclusion criteria

Patients who meet the following criterion are not included.

1. Patients with documented diagnosis of bronchial asthma, asthma-COPD overlap syndrome (ACOS), bronchiectasis, cystic fibrosis, or lung cancer

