9.3.3.7 Treatments

Treatments for COPD will be recorded in the CRF within the retrospective duration, including medications related to COPD, rescue treatments, and oxygen therapies, etc.; of which, prescription date, doses, frequency, the route of administration, and reasons for switching medications will be recorded. Above information (except for rescue treatments) will be recorded every 6 months from 6 months before the index date until death or 1 year after the index date, whichever occurs first.

In addition, pharmacological therapies for comorbidities will also be documented and information will be recorded every 6 months from 6 months before the index date until death or 1 year after the index date, whichever occurs first.

- Related to COPD:

Medications of interest

- SABA: fenoterol, salbutamol, and terbutaline
- SAMA: ipratropium bromide
- LABA: indacaterol and olodaterol
- LAMA: aclidinium bromide, glycopyrronium, and tiotropium, umeclidinium
- LABA + LAMA: tiotropium/olodaterol, indacaterol/glycopyrronium, and vilanterol/umeclidinium (FDC)
- LABA + ICS: formoterol/bclomethasone, formoterol/budesonide, salmeterol/fluticasone, and vilanterol/fluticasone

Proprietary confidential information © 2019 Boehringer Ingelheim International GmbH or one or more of its affiliated companies

- Triple therapies: free combo or vilanterol/umeclidinium/fluticasone (FDC)
- Others: theophylline, roflumilast, and mucolytics, etc.

Rescue treatments

Therapies for the emergency or hospitalization regarding COPD will be collected, including but not limited to the following list:

- Short-acting bronchodilators: SABA (fenoterol, salbutamol, or terbutaline) or SAMA (ipratropium bromide)
- Antibiotics, only record those for respiratory infections
- Oral corticosteroid: prednisone or prednisolone
- Ventilator support: noninvasive (nasal/facial mask) or invasive (orotracheal tube or tracheostomy), or oxygen therapies

Others

Non-pharmacological therapies, including but not limited to the following:

- Oxygen therapy: collecting the therapy for maintenance such as noninvasive positive pressure ventilators (NIPPV) or intermittent positive pressure ventilation (IPPV)
- Surgery, especially relating to COPD or improving the lung function
- Related to comorbidities

Pharmacological therapies for comorbidities of interest (see **Section 9.3.3.2**) will be collected.

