9.7.1 Main analysis

The propensity score matching approach* will be used to balance the baseline characteristics between the study cohorts. These data will be compared descriptively between patients receiving different regimens (Tio + Olo vs. other LABA/LAMA vs. LAMA). If the propensity score matching is done, the difference before and after matching will be considered both.

For the primary outcome

Time to the first moderate or severe COPD exacerbation will be compared between different cohorts using Kaplan-Meier curves with the incidence and time to events, and statistical significance will be assessed using log-rank tests.

Time to first acute exacerbation starts from the index date to the date of the first acute exacerbation recorded on the CRF. Patients with exacerbation free at the time of escalating to ICS or no documented with exacerbations will be censored.

For secondary outcomes

- Time to escalating to dual/triple therapy will also be analysed using Kaplan-Meier curves and log-rank tests.
- The annualized rate of exacerbation with various severity will be calculated for each study group (episodes/patient-year), and the differences between the three cohorts will be compared by rate ratio.
- Results of lung function (i.e., spirometry data) and COPD assessments (i.e., CAT and mMRC) will be evaluated by the change from baseline. Pair *t*-test or other applicable statistical methods will be used for assessing the intra-group difference under a significance level of 0.05.
- Chi-square test or Fisher's exact test will be applied for categorical variables such as reasons for switching/escalating therapies, frequency, and percentage, etc.

*NOTE: Variables may include but not limited to age, gender, disease duration before index date, smoking status, body mass index, COPD assessment score (e.g., CAT and mMRC), spirometry data (e.g., FEV₁), oxygen therapy, comorbidities, disease severity, previous exacerbation, previous treatments, or eosinophil counts, where appropriate.

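### The abstract's censoring sentence omits LAMA as a switch destination, so step-up is censored but step-down is not, and product swaps are handled differently in cohort C than in A and B

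*Combined protocol and SAP*

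**What the plan says.** Section 9.2.2 defines cohort A as Tio + Olo, B as other LABA/LAMA therapy and C as LAMA therapy. Section 9.1 assigns patients by the prescription on the index date.

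The abstract's Study design entry then gives one censoring sentence for everyone: "Patients will be censored at the time from one LAMA/LABA or LAMA switched to another LAMA/LABA or ICS". Follow-up otherwise runs "until the date of death or 1 year after the index date, whichever occurs first".

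Section 9.7.1 has a narrower sentence for the primary outcome: "Patients with exacerbation free at the time of escalating to ICS or no documented with exacerbations will be censored". It does not mention product swaps, step-down or stopping.

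Product changes inside a class are possible in both B and C. Section 9.3.3.7 lists four single-agent choices ("LAMA: aclidinium bromide, glycopyrronium, and tiotropium, umeclidinium") and three fixed combinations ("LABA + LAMA: tiotropium/olodaterol, indacaterol/glycopyrronium, and vilanterol/umeclidinium (FDC"), two of which belong to cohort B. The inclusion criteria also admit free combinations. Section 9.3.1, where on-treatment time could have been defined, is marked not applicable.

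**The concern.** The abstract has chosen to censor at some treatment changes, which is an on-treatment idea. Such a rule is only neutral between cohorts if leaving the index regimen is handled the same way whichever direction the patient goes. Here the list of destinations contains LABA/LAMA and ICS but not LAMA. The two cohort classes that patients can move between are LABA/LAMA and LAMA, so moves one way are censored and moves the other way are not.

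What is at stake is who counts as at risk in the Kaplan-Meier and log-rank comparison of time to first moderate or severe exacerbation, and which episodes and person-time enter the rate ratios. Propensity matching on baseline variables cannot correct a difference created after the index date. The plan itself gives worsening exacerbation as an example reason for escalating, so switching may be related to outcome.

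**Working it through.** There is no planned figure to reproduce; the point rests on how a rule is worded. I applied the abstract's sentence to each possible change.

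**Step 1: read the rule.** Origins: a LABA/LAMA, or a LAMA. Destinations: another LABA/LAMA, or ICS. A change is censored only if its destination is listed.

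**Step 2: apply it.**

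| Change after index | Cohort A | Cohort B | Cohort C |
|---|---|---|---|
| To a different LABA/LAMA | censored (product swap, leaves A) | censored (product swap, within B or to Tio + Olo) | censored (step-up) |
| To a LAMA, or a different LAMA | not listed (step-down) | not listed (step-down) | not listed (product swap within C) |
| To an ICS-containing regimen | censored | censored | censored |
| Stopping | not listed | not listed | not listed |

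Each row is uniform, so formally there is one rule. But row 1 is a swap for A and B and a step-up for C, while row 2 is a step-down for A and B and a swap for C. Hence step-up is censored and step-down is not, and swaps are censored in A and B but not in C. A patient reduced from Tio + Olo to tiotropium alone is on cohort C's regimen but still counted in A; a patient raised from tiotropium to Tio + Olo is censored from C. Rows 3 and 4 show no difference between cohorts. A move to LABA alone is also unlisted.

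**Step 3: look for a repair elsewhere.** Section 9.7.1 censors at escalation to ICS only. If that sentence governs, neither step-up to LABA/LAMA nor step-down nor any product swap is censored, so the asymmetry goes, but time on another cohort's regimen stays in the starting cohort in both directions. If the abstract's sentence is carried into 9.7.1, the asymmetry goes with it. No other visible section covers these changes.

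**Step 4: scale, with assumed inputs only.** The documents give no switching, step-down or stopping rates. The sums below concern annualized rates, not the log-rank test.

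*A versus C, step-down.* Section 9.5 gives 0.78 per patient-year for Tio + Olo and 0.90 for other therapies. Assume 0.90 for cohort C and for A patients after step-down, and assume a share f of A's person-time falls after step-down. Ratio = [(1 − f) × 0.78 + f × 0.90] / 0.90.
- f = 0: 0.78 / 0.90 = 0.867
- f = 0.10: (0.702 + 0.090) / 0.90 = 0.880
- f = 0.30: (0.546 + 0.270) / 0.90 = 0.907

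*B versus C, product swaps.* Assume identical cohorts in which 20% swap product at mid-year and have twice the rate r of the rest.
- Swaps censored (B): (0.8r + 0.2 × 0.5 × 2r) / (0.8 + 0.2 × 0.5) = 1.0r / 0.9 = 1.111r
- Swaps not censored (C): 0.8r + 0.2 × 2r = 1.2r
- Apparent B:C ratio: 1.111 / 1.2 = 0.926, where the truth is 1

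*A versus B, same assumptions.* Both cohorts are censored at the swap: 1.111r / 1.111r = 1.00, so no distortion.

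**The case against.** The strongest reply has several parts.

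- **It is one loosely drafted abstract sentence, and non-censoring is inferred from silence.** True, and the omission may be accidental. One could even read the slash in LAMA/LABA as meaning either drug, which would bring LAMA in as a destination. But the same sentence lists LAMA separately from LAMA/LABA as an origin, so the slash most naturally means the combination. Either way, the analyst is left to decide after seeing data.
- **Section 9.7.1 is the analysis text and overrides the abstract.** If so, the asymmetry disappears, as step 3 shows. That makes this part of the same reconciliation, but choosing between the two sentences still leaves step-down, swaps and stopping unsettled.
- **Keeping post-switch time in the starting cohort is a recognised choice, and censoring at step-down can itself be informative.** Both stand. They argue for reporting an analysis without switch censoring, not for censoring in one direction.
- **Section 9.7.2 is redacted.** It may contain further analyses; the conclusion here covers only the visible text.

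Three stronger readings are tempting and are not supported. First, that censored swaps flatter B alone, including against A: moves from Tio + Olo to another LABA/LAMA are censored too, so A versus B is even-handed. For the same reason, the 0.926 illustration should not be set against the planned 13% difference in section 9.5, whose sample sizes are Tio + Olo against other LABA/LAMA. Second, that stopping is handled differently by cohort: the sentence is silent on stopping for all three. Third, that the dilution figures are estimates: the documents state no rate for cohort C, for LAMA after step-down, or for no treatment.

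**Conclusion.** The point holds on the literal wording of the abstract: LAMA is missing as a switch destination, so A and B time after step-down to cohort C's regimen remains in A and B, while C time ends at step-up, and product swaps are handled differently in C than in A and B. The comparisons affected are A versus C and B versus C. A versus B is handled alike on product swaps.

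The size is unknown. The ratios of 0.880 to 0.907 (A versus C) and 0.926 (B versus C) show only what the assumed inputs would produce. The direction is not fixed either: if stable patients are the ones stepped down, the retained time would favour A and B rather than dilute them. For the primary outcome, only changes before the first moderate or severe exacerbation matter. The plan should be corrected, because the issue touches the primary comparison and is inexpensive to settle before analysis.

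**What to change.** When the abstract and section 9.7.1 are reconciled, state one censoring rule in 9.7.1 for both the primary outcome and the exacerbation rates, and repeat it unchanged in the abstract:

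- In all three cohorts, censor at the first switch from the index product to another LABA/LAMA, to a LAMA (step-down or a different LAMA), or to an ICS-containing regimen. Say in the same sentence how a move to LABA alone is treated.
- Do not exempt swaps within B while censoring moves from A to a B product. Under the assumptions in step 4, that would give 1.111r / 1.2r = 0.926 for A versus B, an apparent advantage for Tio + Olo created by the rule.
- Handle stopping identically in every cohort, for example as a sensitivity analysis using the recorded stop dates.
- Report an analysis without switch censoring alongside, and give the number and timing of each type of switch by cohort.

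The cost is mainly wording. Prescription dates and switch reasons are collected (section 9.3.3.7), and start and stop dates are listed in the abstract's variables. Two limits apply. COPD treatments are recorded at 6-month intervals, so the team should confirm that switch dates can be recovered. Days of supply are not among the listed fields, and collection was planned to end on 30 November 2019, five days after this version's date, so the rule should not depend on new data. The statistical price is somewhat more censored time, which may be informative; this is why the analysis without switch censoring is needed.
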